4.5 Prior and Concomitant Therapy

Before first administration of study drug, subjects must not have received anticancer medications or investigational drugs within the intervals defined in Section 3.2.2, exclusion criterion #7. Subjects will not be permitted to receive any other anticancer-related therapy during the study.

4.6 Investigational Agent Accountability

International regulatory agencies require accounting for the disposition of all investigational product received by each investigative site. Information on investigational product disposition required by law consists of the date received, date administered, quantity administered, and the subject to whom the investigational product was administered. The principal investigator (or designee, as specified in the Delegation of Authority Log) is responsible for accounting for all unused investigational product and all used investigational product containers. Investigational product may not be given to non–study participants under any circumstances.

Supplies will be shipped to the investigative site at appropriate intervals, depending on subject accrual. The site will use either the Investigational Product Dispensing Form provided by Agenus or a similar standard form approved by Agenus to document investigational drug disposition. This form must be maintained either in the pharmacy or in another area approved by the Agenus monitor. The monitor will review investigational product accountability during routine monitoring visits.

At the termination of the study, a final investigational product accountability review and reconciliation must be completed, and any discrepancies must be investigated and their resolution documented.

5. Study Procedures and Assessments

5.1 Schedule of Assessments

The schedule of assessments is provided in Table 10.

Confidential Page 47 of 78

Table 10: Schedule of Assessments

	Screening		Treatment and Evaluation								Disease Assessments	End of Treatment Visit	Final Safety Visit	Survival F/U	
Study Week		1	2	4		7		10		12	Q3, 6, and 12W after Week 12	After disc. of treatment	28 days after last dose	90 days after last dose	Every 12 weeks until death or for up to 2 years
Visit Window (days)	Within 28 d of first dose		± 2	± 3		± 3		± 7		± 2	± 7	± 7	± 7	± 7	± 14
Assessment		D1 C1	D8 C1	D1 C2		D1 C3		D1 C4		D15 C4					
Informed consent	X														
Review of eligibility criteria	X	X													
Medical history a	X														
NYHA class evaluation	X														
Tumor biopsies/archival tissue collection ^b	X					X									
12-lead ECG ^c	X	X		X								X	X	X	
Performance status (ECOG)	X	X		X		X		X			X	X	X	X	
Physical examination	X	X		X		X		X			X	X	X	X	
MRI or CT disease assessment by RECIST ^d	X					X				X	X d	X	X	X	
AGEN1884 administration ^e		X		X		X		X			X				
Serum chemistry f	X	X	X	X		X		X			X	X	X	X	
Endocrine function tests (free T4, TSH and ACTH) ^f	X	X	X	X		X		X			X		X		
Hematology f	X	X	X	X		X		X		•	X	X	X	X	
Tumor marker assessment g	X	X		X		X		X			X	X	X	X	
Urinalysis ^f	X	X	X	X		X	T	X			X	X	X	X	
Coagulation ^f	X	X	X	X		X		X			X	X	X	X	

Confidential Page 48 of 78

	Screening		Treatment and Evaluation									Disease Assessments	End of Treatment Visit	Final Safety Visit	Survival F/U		
Study Week		1	2		4			7			10	12	Q3, 6, and 12W after Week 12	After disc. of treatment	28 days after last dose	90 days after last dose	Every 12 weeks until death or for up to 2 years
Visit Window (days)	Within 28 d of first dose	l	± 2		± 3			± 3			± 7	± 2	± 7	± 7	± 7	± 7	± 14
Assessment		D1 C1	D8 C1		D1 C2			D1 C3			D1 C4	D15 C4					
Adverse events	X	X	X		X			X			X	X	X	X	X	X	
Pregnancy test h	X	X			X			X			X		X		X	X	
Concomitant medications	X	X	X		X			X			X	X	X	X	X	X	
Vital signs i	X	X i	X		X i			X^{i}			X i	X	X i	X	X	X	
Evaluation of DLTs (phase 1 dose escalation only)		X	X		X												
PGx (whole blood) j	X																
Blood sample for serum PK and/or ADA k		X	X		X			X			X	X			X	X	
Survival follow-up and initiation of subsequent therapy																	X

ACTH: adrenocorticotropic hormone; ADA: anti-drug antibody(ies); AFP: alpha-fetoprotein; C: cycle; CA-125: cancer antigen 125; CR: complete response; CT: computed tomography; D: day; disc: discontinuation; DLT: dose-limiting toxicity; ECG: electrocardiogram; ECOG: Eastern Cooperative Oncology Group; F/U: follow-up; FFPE: formalin-fixed paraffin-embedded; HCC: hepatocellular carcinoma; IV: intravenous; MRI: magnetic resonance imaging; NYHA: New York Heart Association; PGx: pharmacogenomics; PK: pharmacokinetic(s); PR: partial response; Q: every; RECIST: Response Evaluation Criteria in Solid Tumors Version 1.1; SD: stable disease; T4: thyroxine; TSH: thyroid stimulating hormone; W: week.

- a. All prior cancer treatments collected as part of medical history.
- b. Biomarker assessment will be performed on the most recent FFPE biopsy of a tumor lesion, preferably collected after progression on the last therapy and/or collected at screening, if clinically feasible. If a recent biopsy is not available, an archival FFPE sample should be provided from a site not previously irradiated. An optional tumor biopsy will be collected at Cycle 3, Day 1 (-3/+1 day), if clinically feasible, to assess pharmacodynamic effects of the drug.
- ^c 12-lead ECG to be recorded at screening (within 7 d of first treatment dose) any time during visit as long as within protocol window. Day 1 of Cycles 1 and 2 to be recorded 1 h ± 30 min following flush of infusion line. Other ECGs to be ordered as clinically indicated by treating physician.
- d. Disease response assessments by RECIST to be performed at Study Week 6, Week 12 and Q6w for subjects assigned to 3- or 6-w treatment schedule, or Q12w for subjects assigned to 12-w treatment schedule until off-disease response evaluation criteria are met.

Confidential Page 49 of 78

- e. AGEN1884 to be administered IV over 60 (-10/+20) min. Subjects with SD, PR, or CR at 12-w evaluation timepoint may continue receiving AGEN1884 every 3, 6, or 12 w (± 7 d) beginning at Study Week 12 for ≤1 year provided they are tolerating study drug. The appropriate schedule will be based on discussion with medical monitor to confirm that proposed schedule is in subject's best interest.
- For screening, laboratory assessments to be completed within 7 d prior to first AGEN1884 administration. Prior to every AGEN1884 administration, laboratory values to be reviewed (with the exception of endocrine function tests). Delay AGEN1884 if any dosing delay criteria are met according to Section 4.1.2.
- g. For tumors with known markers (e.g., AFP for HCC, CA-125 for ovarian cancer, etc.), samples to evaluate tumor marker levels at sites at screening and at each tumor assessment.
- h. Women of childbearing potential only. Serum pregnancy test to be performed at screening (within 7 d of first AGEN1884 treatment); urine pregnancy tests to be performed at subsequent visits.
- Vital sign measurements to be collected within 30 min prior to administration, every 30 (± 10) min during the 60-min AGEN1884 infusion, including at end of 15-min flush of infusion line (± 15 min). This equates to 4 sets of vitals over the course of a 60-min infusion and flush, including pre-administration vitals. A final set of vitals will be collected 1 h (± 15 min) following flush of infusion line, unless otherwise indicated.
- Blood sample for PGx is collected only if an optional PGx consent is signed.
- For Cycles 1, 2, 3, 4, 5, 8, 12, and 16, blood samples for serum PK and ADA analyses to be collected on Day 1 predose (within 1 h predose). For Cycles 1 and 4, a blood sample for serum PK analysis is to be collected on Day 1 at 2 (±0.25) h post start of AGEN1884 infusion. The 2 h postdose PK sample should never be taken during any study drug infusion, but within 1 h following end of the infusion (for those study drug infusions that go longer than the protocol recommended durations). A blood sample for serum PK analysis will also be collected at Cycle 1 Day 8 (168 ±4 h post start of AGEN1884 infusion). Blood samples for serum PK and ADA analyses are to be collected at the End of Treatment Visit and the Final Safety Visit. See Table 11 for additional PK sampling in an approximate 20 subject subpopulation.

Confidential Page 50 of 78

5.1.1 Screening

Subjects will undergo screening assessments specified in the schedule of assessments (Table 10) within 28 days prior to the first dose of AGEN1884. Laboratory assessments (including serum pregnancy) and ECG should be performed within 7 days prior to first treatment dose of AGEN1884.

Subjects who fulfill all of the inclusion criteria and none of the exclusion criteria will be enrolled into the study. Subjects who do not meet the inclusion and exclusion criteria will be considered screen fails, and their demographic information and reason for screen failure should be documented.

5.1.2 Treatment and Evaluation Period

Subjects will be treated as described in the schedule of assessments (Table 10) and evaluated for pharmacodynamics, PK, immune correlates, disease response, and safety. If a subject discontinues for reasons other than PD, tumor assessments will continue until PD occurs or other criteria for discontinuation are met.

5.1.3 End-of-Treatment Visit

The End-of-Treatment Visit should occur at the time study drug is discontinued for any reason. The End-of-Treatment Visit occurs 28 days from the last dose of study treatment.

5.1.4 Final Safety Visit

The mandatory Safety Follow-Up Visit should be conducted for all subjects approximately 90 days after the last dose of study drug or before the initiation of a new antineoplastic treatment, whichever comes first. Subjects with an AE of Grade >1 will be further followed until the resolution of the AE to Grade 0-1 or until beginning of a new antineoplastic therapy, whichever occurs first. Subjects with an ADR ongoing at the Safety Follow-up Visit must be followed up until the ADR resolves, becomes stable, or is considered not clinically significant by the investigator.

5.1.5 Survival Follow-up

Subjects who discontinue study treatment will be followed for survival by phone contact every 3 months. Survival follow-up will continue until death, for up to 2 years, or until study closure. Subjects will also be followed for initiation of another cancer therapy.

If a subject withdraws from the interventional portion of a study and does not consent to continued follow-up of associated clinical outcome information, the investigator will not access for purposes related to the study the subject's medical record or other confidential records requiring the subject's consent. However, investigators will consult public records, such as obituaries and the Social Security index to establish survival status.

5.2 Demographics and Screening Procedures

5.2.1 Demographics and Medical/Cancer History

The subject's date of birth, gender, race, and ethnicity are to be documented.

A full medical history is to be documented during the screening visit by the investigator or designated participating physician and may include medical notes documented by a referring

Confidential Page 51 of 78

physician in the subject's medical record. The medical history is to include any current active diagnoses and any previously treated illnesses, including the approximate date of onset (at minimum indicate the year or approximate year) and date of resolution if applicable, and description of any prior surgeries. The body systems to be reviewed and any concurrent or past diagnoses documented include but are not limited to: eyes, ears, nose, and throat; respiratory; cardiovascular; gastrointestinal; musculoskeletal; neurological; endocrine/metabolic; hematologic/lymphatic; dermatological; genitourinary; psychiatric; and allergies.

Baseline information about the malignancy, including type of cancer, date of diagnosis, and prior treatments, will also be collected.

5.2.2 Eastern Cooperative Oncology Group Scale

Subjects will be graded according to ECOG performance status score (Appendix C).

5.2.3 New York Heart Association Class Evaluation

The NYHA class will be evaluated at screening (Appendix D).

5.2.4 Tumor Markers

For tumors with known markers (e.g., alpha-fetoprotein [AFP] for HCC, cancer antigen 125 [CA-125] for ovarian cancer, etc.), samples to evaluate levels of tumor markers will be obtained at screening and at each tumor assessment.

5.3 Pharmacokinetic Assessments

Serum AGEN1884 concentrations will be determined by validated methods. PK parameters to be estimated and reported may include, but may not be limited to, maximum observed drug concentration at steady-state (C_{max-ss}), minimum observed drug concentration at steady-state (C_{min-ss}), area under the drug concentration-time curve within time span t1 to t2 at steady-state ($AUC_{(t1-t2)-ss}$), area under the drug concentration-time curve from time of dosing to time of last observation ($AUC_{(0-t)}$), area under the drug concentration-time curve from time of dosing extrapolated to infinity ($AUC_{(0-\infty)}$), time to reach maximum drug concentration (t_{max}), terminal elimination rate constant (λ_z), terminal elimination half-life ($t_{1/2}$), systemic clearance (CL), and volume of distribution (Vd). PK parameters will be summarized using descriptive statistics. Individual as well as summary drug concentration-time profiles will be depicted. Unresolved missing data may be imputed when analysis integrity is affected. The conservative principle will be used for data imputation. Both noncompartmental (NCA) and compartmental modeling (e.g., population pharmacokinetics [PopPK]) techniques will be used to analyze the pharmacokinetics. Sampling times for all subjects are shown in Table 10.

In addition to the PK sampling times for the general population shown in Table 10, a subgroup of approximately 20 subjects will have samples taken at 3 additional timepoints shown in Table 11.

Confidential Page 52 of 78

Table 11: Additional Pharmacokinetic Sampling Schedule in an Approximate 20 Subject Subpopulation

Cycle	Sampling Times
Cycle 1	D3 (48±4 h)
Cycle 4	D3 (48±4 h); D8 (168±4 h).

Blood samples collected Days 3 and 8 at 48±4 h and 168±4 h, respectively, after the *start* of the infusion.

Unresolved missing data may be imputed when analysis integrity is affected. The conservative principle will be used for data imputation.

5.4 Immunogenicity Assessments

Serum AGEN1884 ADA monitoring will be conducted via blood serum samples collected prior to drug administration, throughout the entire course of drug administration, and at the final safety visit. Sampling times are shown in Table 10.

5.5 Exploratory Biomarkers

To better understand the pharmacodynamics of AGEN1884, a correlation with additional biomarkers may be necessary, this includes but may not be limited to whole blood, plasma, and serum samples for exploratory biomarker analysis according to the schedule of assessments (Table 10) as well as tumor tissue collected at screening and an optional on-treatment biopsy.

Within this trial, additional biomarker assessments that might be correlated with safety, response, or resistance to treatment beyond those listed (e.g., monitoring inflammatory or immune markers, measuring specific cell populations, or measuring cell surface markers by flow cytometry, immunoblot, mass spectroscopy, immunoassay, tumor markers, or correlations between drug exposure and/or response including tumor mutational burden and other variations in deoxyribonucleic acid [DNA] or in ribonucleic acid [RNA] [pharmacogenomics]) may be evaluated at the discretion of the Sponsor using excess PD, PK, whole blood, plasma, serum, or biopsy samples. Participation in pharmacogenomics (PGx) studies involving the analysis of DNA and/or RNA is optional and requires separate informed consent (Section 7.1).

Ongoing research may lead to the identification of new important markers related to anti-CTLA4 therapies and/or safety in a near future; therefore, each subject will also be asked whether any remaining tumor tissue or blood-derived samples can be stored at a central repository and can be used for future exploratory research on the drug and / or disease-related aspects. A subject's consent to the use of any remaining samples for such future exploratory research shall be optional and shall not affect the subject's participation in the current trial. After analysis by the Sponsor or its designee, samples will be maintained for up to 5 years following completion of the study and will then be destroyed unless the subject withdraws consent or requests that his/her sample/results be destroyed. During this 5 year period, samples may be reanalyzed by the Sponsor or its designee, collaborator, or partner.

Confidential Page 53 of 78

5.6 Pharmacodynamic Assessments and Biopsy

5.6.1 Biopsy and Tissue Collection

Tumor tissue for biomarker analysis from a biopsy of a tumor lesion not previously irradiated must be available for biomarker assessments. Biomarker assessment will be performed on the most recent FFPE biopsy of a tumor lesion, preferably collected after progression on the last therapy and/or collected at screening, if clinically feasible. If a recent biopsy is not available, an archival FFPE sample should be provided from a site not previously irradiated. An optional tumor biopsy will be collected at Cycle 3, Day 1 (-3/+1 day), if clinically feasible, to assess pharmacodynamic effects of the drug.

Tissue from needle or excisional biopsy or from resection is required.

Preferably, an FFPE tumor tissue block should be provided. If the tumor-containing FFPE tissue block is not available, 25 sections (slides) \leq 1 month old should be provided; \geq 15 slides are required. If no tumor tissue is available, a fresh biopsy will be required, if clinically feasible.

Fine needle aspirates, endobronchial ultrasound (EBUS) or cell blocks are not acceptable.

If a tumor biopsy was obtained from a target lesion during eligibility assessment, it is preferred to obtain a new baseline scan. Biopsy of lesions on study should be limited to non-target lesions or new lesions if their pathologic etiology is ambiguous.

Tissue processing: The cancer tissues should be fixed in 10% neutral buffered formalin, paraffin embedded, and routinely processed for histological evaluation. Formalin substitutes are not suited as fixative.

Provision of samples:

- 1. Priority: tumor containing FFPE tissue block;
- 2. Priority: if the tumor containing FFPE tissue block cannot be provided in total, sections from this block should be provided that are freshly cut (within the last month), 5 μm thick, and mounted on SuperFrost Plus microscope slides. Preferably, 25 slides should be provided; if not possible, a minimum of 15 slides are required. The SuperFrost Plus microscope slides and slide containers will be provided by the central lab.

Sample shipment: The tumor blocks and freshly prepared slides should be sent with the next shipment to the central lab.

Sample storage: At the central laboratory, the FFPE tissue blocks shall be stored at room temperature in the dark and the FFPE tumor slides shall be kept in sealed containers at 2°C to 8°C.

For additional details and instructions regarding tissue requirements, collection, storage and shipment, refer to the study Laboratory Manual.

5.6.2 Pharmacogenomics (Optional)

The sponsor may conduct research on DNA (blood) or tumor tissue specimens collected during this trial. This research may include genetic analysis (DNA) and gene expression profiling (RNA). Such research is for pharmacogenomic testing to address emergent questions not described elsewhere in the protocol (as part of the main trial) and will only be conducted on

Confidential Page 54 of 78

specimens from appropriately consented subjects. The overarching goal is to develop safer, more effective drugs.

Germline (inherited) variants will be investigated in DNA extracted from the whole blood. For this purpose, an additional 4 mL of whole blood (PGx sample) will be collected at screening. Additionally, tumor biopsy samples may be used for the extraction of DNA to study tumor genetics (somatic variations). Participation is optional for subjects being recruited at sites whose IEC/IRB has approved PGx assessments and a PGx informed consent form (ICF) (optional) is signed (Section 7.1).

All samples collected during the trial will be kept confidential. For this purpose, the samples will be given a label connected with a code assigned at the start of the Main Study (coded trial subject number). Outside the study center, no one will be able to link the subject's identity to the subject number. The link between the subject's identity and the subject number will only be known by a limited number of authorized personnel. Information about race, ethnicity, sex, medical history, etc., may be available to scientists studying the PGx blood samples. Such information might be important for research or public health purposes. Genomic analysis results will not be reported back to the sites.

Participation in PGx portion of the trial is optional and requires separate informed consent. Participation in the PGx portion of the trial will not affect participation in the trial. Subjects may withdraw consent from PGx portion of the trial without withdrawing from the trial. Consent and withdrawal of consent (if applicable) for PGx assessments will be documented in the eCRF.

5.7 Tumor Assessments

5.7.1 Response Evaluation Criterion in Solid Tumors

Primary disease assessments will be performed based on RECIST Version 1.1 (Appendix E). Disease response assessments by RECIST to be performed at Study Week 6, Week 12 and Q6w for subjects assigned to 3- or 6-w treatment schedule, or Q12w for subjects assigned to 12-w treatment schedule until off-disease response evaluation criteria are met.

Assessment of tumor size (by magnetic resonance imaging [MRI] or computed tomography [CT] scan) will be performed as specified in the schedule of assessments (Table 10) until disease progression is determined by RECIST or other off—tumor evaluation criteria are met. The same modality should be used for each subject through the course of his or her disease evaluation. Treatment cycles may become out of sync with tumor assessments if a delay in therapy is indicated; however, in this event, tumor assessments will remain on the original schedule.

Subjects who discontinue study drug for a reason other than disease progression will continue to be assessed for their disease status per the schedule of events and should continue to have tumor assessments every 6 weeks, or per disease-specific schedule, until further disease progression (additional 10% from first PD observation), death, or the end of the study.

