3.5 Discontinuation of Therapy

Treatment with AGEN1884 should be discontinued if 1 of the following primary reasons occur:

- Unacceptable toxicity (based on the investigator's clinical decision that the subject is unable to tolerate therapy).
- Adverse event
- Radiographic progression of disease (compared to baseline assessment). Disease progression is defined as progression confirmed by a second, consecutive assessment ≥6 weeks apart.

Note: If subject with evaluation of disease progression is having clinical benefit despite the progression, treatment may continue following discussion with, and approval of the medical monitor.

- Investigator decision
- Clinical progression of disease
- Protocol deviation
- Subject completed treatment
- Investigator decision
- Subject noncompliance with protocol for nonmedical reasons

Subjects who discontinue therapy prior to progression should continue to be followed for response and complete disease assessments every 12 weeks according to standard of care for up to 2 years from first AGEN1884 administration. Subjects will be followed for safety ≥90 days following the last administration of investigational agent, as described in Section 5.8.

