8.7.6 Progression-Free Survival

Progression-free survival (PFS) is defined as the interval from the date of first dose of investigational agent until the earliest date of PD per RECIST 1.1 or death due to any cause within 90 days (i.e., 12 weeks+6 days) of last tumor assessment (if no progression is documented). If a patient transitioned to a new anti-cancer therapy, any time point assessment(s) and death(s) that happened after that will be disregarded.

The primary analysis will be performed ignoring transient PDs, using the same definition of transient PDs as in Section 8.7.1. Thus, the terminating event will be a non-transient PD or death, whichever occurs first. Patients who did not experience a non-transient PD or death will be censored on the date of last evaluable tumor assessment, the date of the last evaluable assessment without any assessment in the following 90 days and then followed by PD or death, or the last evaluable assessment performed before initiation of new anti-cancer therapy (if applicable), whichever comes earlier.

The alternative (sensitivity) analysis will be performed for terminating event of death or first observed time-point PD, whichever occurs first. Censoring will be on the date of last evaluable tumor assessment, the date of the last evaluable assessment without any assessment in the following 90 days and then followed by PD or death, or the last evaluable assessment performed before initiation of new anti-cancer therapy (if applicable), whichever occurs first.

PFS will be reported in months. Median PFS will be provided (estimated using K-M estimate, with 95% CI) and Kaplan-Meier curves of PFS will be plotted.

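### The off-treatment scan interval defaults to 12 weeks in Protocol 3.5 but 6 weeks in 5.7.1, and the SAP's 90-day gap rule can censor a progression found at an in-window 12-weekly scan

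*Protocol*

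**What the plan says.** Two protocol sections cover the same subjects.

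- **Protocol 3.5:** "Subjects who discontinue therapy prior to progression should continue to be followed for response" and are to "complete disease assessments every 12 weeks according to standard of care for up to 2 years from first AGEN1884 administration".
- **Protocol 5.7.1:** "Subjects who discontinue study drug for a reason other than disease progression will continue to be assessed for their disease status". On the interval, it says that they "should continue to have tumor assessments every 6 weeks, or per disease-specific schedule". For the stopping point, it has scanning run on "until further disease progression (additional 10% from first PD observation), death, or the end of the study".

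Two other places touch the question without answering it.

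- **Protocol 5.1.2** says, for subjects who stop for reasons other than progression, that "tumor assessments will continue until PD occurs or other criteria for discontinuation are met". It gives no interval.
- **Protocol Table 10** marks a scan after discontinuation and at the visits 28 and 90 days after the last dose, with no repeat interval off treatment. Its footnote d ties the interval to the assigned treatment schedule: 6-weekly for the 3- and 6-week schedules, and "Q12w for subjects assigned to 12-w treatment schedule until off-disease response evaluation criteria are met".

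PFS and DOR end at radiographic progression or death (Protocol 6.2.1.2; SAP 4.5). For PFS, SAP 8.7.6 censors at the "last evaluable assessment without any assessment in the following 90 days" when progression or death then follows. SAP 8.7.2 applies the same rule to DOR. Both sections gloss 90 days as 12 weeks plus 6 days.

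**The concern.** Progression is dated at the scan that finds it, so the scan interval is part of how PFS and DOR are measured. Two sites reading different sections could follow comparable subjects at intervals that differ twofold, and the pooled Kaplan-Meier curves would mix the two.

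The gap rule is a second problem. Its limit lies 6 days beyond a 12-week interval, while the visit window is 7 days either side. A subject scanned exactly as the protocol allows can therefore have a progression replaced by censoring at the previous scan. The rule also depends on the outcome. It applies only when progression or death follows the gap, so a clean scan on day 91 keeps the subject in follow-up while a progression on day 91 is removed. Removing events in this way tends to raise PFS and DOR.

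**Working it through.** **Inputs.** Intervals of 84 days (Protocol 3.5; Table 10 footnote d for the 12-week schedule) and 42 days (Protocol 5.7.1). Window of ±7 days for scans after Week 12 and after discontinuation (Table 10, as read from the extracted table). Gap limit of 90 days (SAP 8.7.2, 8.7.6). The plan states no figure of its own to reproduce.

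**1. Do the sections cover the same subjects?** Stopping therapy before progression (3.5) and stopping drug for a reason other than progression (5.7.1) describe one group. No precedence rule is given.

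**2. Detection delay.** The maximum delay equals the interval. The average is about half of it if progression is equally likely at any time between scans.

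| Default | Maximum | Average | Scans, Week 12 to Week 104 |
|---|---|---|---|
| 6-weekly | 42 days | 42/2 = 21 days (0.69 months) | 15 |
| 12-weekly | 84 days | 84/2 = 42 days (1.38 months) | 7 |

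**3. Illustrative effect on a median.** A simulation took subjects who are all off drug and progression-free at the Week 12 scan, with exponential residual time to progression, dated at the next scheduled scan. The residual medians are assumptions; the documents give none. The Table 10 scans at 28 and 90 days after the last dose are left out.

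| Assumed residual median (months) | Recorded median PFS, 6-weekly | Recorded median PFS, 12-weekly |
|---|---|---|
| 2 | 5.52 | 5.52 |
| 4 | 6.90 | 8.28 |
| 6 | 9.66 | 11.04 |
| 12 | 15.18 | 16.56 |

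The median moves by 0 or by one 6-week step (42/30.4375 = 1.38 months). The mean recorded date moves by 0.72 to 0.85 months.

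**4. The gap rule under 12-weekly scanning.**
- Previous scan on its target day, next scan 7 days late: 84 + 7 = 91 > 90.
- Previous scan 7 days early, next scan 7 days late: 84 + 14 = 98 > 90, with both scans in window.
- If each date is uniform over its 15 allowed days, the gap exceeds 90 when the two offsets differ by at least 7 days. That is 8 + 7 + 6 + 5 + 4 + 3 + 2 + 1 = 36 of 15 × 15 = 225 pairs, or 16%. If only the later scan varies, it is 1/15, about 7%.
- Under 6-weekly scanning the longest in-window gap is 42 + 14 = 56 days, so the figure is 0%.

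**5. Early period off drug.** The 28- and 90-day visits are 62 days apart, or at most 62 + 14 = 76 days. The gap rule is not triggered between them.

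**The case against.** The strongest reply is that the conflict is softer than two bare numbers suggest. Section 3.5 defers to standard of care and 5.7.1 allows a disease-specific schedule, so a site whose disease-specific schedule is 12 weeks complies with both. This stands: the sections set different defaults, not mutually exclusive orders. It does not reconcile the defaults, because a site with no disease-specific schedule still has two.

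Nor are the stopping points wholly incompatible. A 2-year cap and a list of stopping events can operate together, and they part mainly for a subject still progression-free at 2 years while the study continues. There is a further difference: 5.1.2 stops at progression, while 5.7.1 runs on to further progression beyond the first.

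The exposed group is also limited. Table 10 scans cover the first 90 days off drug, assessments after new anti-cancer therapy are disregarded, SAP 6.5 admits unscheduled and out-of-window imaging, and subjects on the 12-week treatment schedule are scanned 12-weekly anyway. All of this stands. A reader might infer from the simulation that study PFS could be off by 1.4 months. The documents do not support that: they do not give the share of subjects exposed, and the simulation treats everyone as exposed.

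Finally, the 90-day limit already allows for a 12-week interval, with 6 days to spare. That is true, but the allowance is shorter than the protocol's own window. It also sits badly with SAP 6.5, which keeps even out-of-window scans in the efficacy analysis.

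**Conclusion.** Both parts hold, and they are separate.

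1. Protocol 3.5 and 5.7.1 set different default intervals and different stopping language for the same subjects, and nothing else in the protocol resolves them. For the subset off drug, progression-free, without new therapy and past the 90-day visit, progression can be dated up to 84 rather than 42 days late, on average about 42 versus 21. This assumes detection only at scheduled scans and even risk within an interval. It bounds the delay for a subset and is not an estimate for the trial.

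2. The 90-day rule is too short for any 12-weekly scanning. In-window gaps reach 98 days, and about 16% exceed 90 if both dates are uniform within ±7 days. A reader might take this as a consequence of the first conflict. It is not: on-treatment subjects on the 12-week schedule face it however 3.5 and 5.7.1 are reconciled. The direction is upward for PFS and DOR; the size cannot be derived from the documents.

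The consequence is moderate. PFS and DOR are secondary, descriptive and single-arm, and the sample size is not inferential, so no treatment contrast depends on this. The medians, the DOR landmark estimates and the subgroup summaries do.

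**What to change.** - **Protocol.** Reconcile 3.5, 5.1.2, 5.7.1 and Table 10 to one off-treatment scan interval and one stopping point. If disease-specific or standard-of-care schedules remain allowed, say so in the same words in each place. This review does not say which interval is right.
- **SAP 8.7.2 and 8.7.6.** Set the gap limit to at least the longest scheduled interval plus both visit windows: 84 + 7 + 7 = 98 days if 12-weekly scanning remains anywhere. Apply the same limit in the clauses that count deaths within 90 days of the last assessment. Every in-window progression then counts as an event.
- **Sponsor's choice.** Whether the limit should also tolerate a missed scan is a different censoring policy. One missed 12-weekly scan gives a gap of 168 ± 14 days, so 98 days would not cover it. A limit beyond two intervals is not needed for the purpose here.
- **If scans are already done.** The SAP limit can still be corrected, or a sensitivity analysis without gap censoring added.

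The cost is protocol and SAP wording plus a minor change to the censoring derivation. Choosing either stated default needs no scan that one section does not already ask for.
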